3.1.2 Pilot Phase Cohort: Physical Therapy Throwing Session

During the Pilot Phase, subjects that have been identified, consented, and enrolled will wear a prototype of IDL's throwing monitor device during the duration of their physical therapy appointment. Subjects will wear the device somewhere on their arm and may or may not be asked to perform throwing movements as part of their rehabilitation regimen. This phase will test if the device is able to detect basic throwing movements and create an accurate pitch count.

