4.2 Study Treatment Phase

4.2.1 Pilot Phase Study Visit

- Informed consent and assent

Subjects will be asked to put on the throwing monitor device prototype at the beginning of their physical therapy session and will wear the device for the duration of the visit or until asked by a member of the study team to remove the device. Subjects will be asked to do the following tasks while wearing the device:

- Complete any physical therapy rehabilitation exercises given by their physical therapist as part of their care
- Complete a limited number of additional throwing exercises within in the limits of the rehabilitation regimen
- Complete athletic history survey (not required to wear device for survey completion)
- Medical record review
- Height and weight measurements if not collected as part of clinical care
- Physical exam if not collected as part of clinical care
- Return throwing device at end of session or earlier if requested by study team

No subject will be asked to complete any motions or tasks that may hinder their rehabilitation regimen.

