4.2.2 Phase 1 Study Visit

At the Epic Sports Biomechanics research facility, subjects will be asked to do the following activities:

- Height and weight measurements
- Physical Exam
- Wear the prototype device and participate in a simulated game
 - Pitch approximately 30-45 times using varying pitch types (fastball, change-up, etc.)
- Complete additional baseball-related movements with full the Epic Sports Biomechanics research facility monitors in a random order, including
 - Field-based overhand throws
 - Runs

- Bat swings
- Catching balls
- Return throwing device at end of session or earlier if requested by study team

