5.1.5 Pilot Phase Throwing Evaluations

Subjects will wear the throwing monitor device prototype during a physical therapy session unless asked by a member of the study team to remove it. They will go through all of their normal physical therapy exercises. In addition, subjects may be asked to do a limited number of additional throwing movements during their physical therapy session. Subjects will not have to interact with the device other than donning and doffing the device. The device will collect motion data for the duration of the session. Subjects will not be asked to complete any additional exercises that could hinder their rehabilitation program. Subjects will be asked to return the throwing monitor device by the end of the study visit.

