5.1.6 Phase 1 Throwing Evaluations

At the Epic Sports Biomechanics research facility, subjects will wear the throwing monitor device prototype during a simulated baseball game, pitching approximately 30-45 times using varying pitch types (fastball, change-up, etc.) as they would within a typical game. In addition, each player will perform a set of other baseball-specific movements (field-based overhand throw, run, bat swing, catch ball) typically seen in baseball play. Participants will be fitted with 51 infrared reflective markers to enable tracking of limb, torso, and head movement while actions are performed. Movement data will be video recorded and recorded with 12 Motion Analysis Raptor IR cameras encompassing a capture volume of 26ft length x 7ft width x 8ft height. A minimum of 3 time-synchronized video cameras placed at different viewing perspectives will also record participants as they perform movements. Subjects will be asked to return the throwing monitor device by the end of the study visit.

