6.3 Statistical Methods

6.3.1 Baseline Data

Data will be analyzed with the goal of determining the feasibility of the approach. The accuracy of movement classification, movement phase segmentation, mapping of sensor reading to biomechanical values, and movement detection will all be quantified. K-fold cross validation will be used to estimate the performance of regressors and classifiers. Regressor performance will be quantified via the mean and standard deviation of error values between predicted biomechanical variable values and actual values as determined from motion capture data. Biomechanical value prediction models will be considered successful if error distributions have mean and standard deviation of less than 5% and 10% respectively of the nominal value. Sensitivity and specificity will be used to quantify the

performance of movement detection and classification algorithms. Movement segment detection will be considered correct if the algorithm identifies 90% of time occupied by the movement. Detection algorithms will be considered successful if they are able to operate with specificity and sensitivity of 95%.

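### The 95% sensitivity and 95% specificity rule in Section 6.3.1 does not bound the error in the throw count, although an accurate pitch count is a stated Pilot Phase aim

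*Combined protocol and SAP*

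**What the plan says.** Section 6.3.1 gives the only numerical success limit for detection: "Detection algorithms will be considered successful if they are able to operate with specificity and sensitivity of 95" (per cent). It also says when a segment counts as found: "Movement segment detection will be considered correct if the algorithm identifies 90% of time occupied by the movement". That sentence concerns true movements and does not define a false detection. The section does not state the unit for specificity, and it sets no limit on count error, predictive value or false throws per session.

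Section 3.1.2 gives the Pilot Phase its purpose: "This phase will test if the device is able to detect basic throwing movements and create an accurate pitch count". Sections 2.2 and 6.2 list validation of simple device measurements as a Pilot objective and endpoint, and Section 2 includes the number of throws in the overall purpose.

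On the mix of movements the documents are only qualitative.
- **Pilot:** Section 5.1.5 says of the subjects, "They will go through all of their normal physical therapy exercises", with the device recording throughout. Section 4.2.1 asks them to "Complete a limited number of additional throwing exercises within in the limits of the rehabilitation regimen". Section 3.1.2 allows that the regimen itself may contain no throws.
- **Phase 1:** Sections 3.1.3 and 4.2.2 describe about 30 to 45 pitches in a simulated game. The other movements come afterwards, and Section 5.1.6 says "each player will perform a set of other baseball-specific movements (field-based overhand throw, run, bat swing, catch ball) typically seen in baseball play", without saying how many of each.

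**The concern.** A throw count is the sum of true throws detected and other movements wrongly called throws. Sensitivity governs the first term relative to the number of throws. Specificity governs the second relative to the number of other movements. A limit on specificity therefore says nothing about false throws as a share of the count until the ratio of other movements to throws is known, and the plan neither states nor restricts that ratio.

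An algorithm could therefore be declared successful under Section 6.3.1 and still miscount throws badly in the setting where Section 3.1.2 wants an accurate count. Because the ratio can differ between children and between settings, the resulting bias could not be removed by a constant correction.

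**Working it through.** **Inputs from the documents.** Sensitivity 95% and specificity 95% (Section 6.3.1); about 30 to 45 pitches per Phase 1 subject (Section 4.2.2). The 95% limits are set without a derivation, and Section 6.4 reports no power analysis, so there is no derived figure to reproduce.

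**Assumptions.** Sensitivity and specificity are per movement, refer to the final throw/non-throw output, and sit exactly at the limit. The ratio r of other movements to throws is not in the documents; the range 1 to 19 is assumed.

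**Formulas, for T throws and rT other movements.**
- Expected count = 0.95 x T + 0.05 x rT.
- Net count error = 0.95 + 0.05r - 1 = -5% + 5% x r.
- PPV = 0.95 / (0.95 + 0.05r).
- Specificity needed for PPV of 95% at 95% sensitivity: false throws may not exceed 0.05T, so specificity must be at least 1 - 0.05/r.

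| r (assumed) | Throws as share of movements | Net count error | PPV | Specificity needed for PPV 95% |
|---|---|---|---|---|
| 1 | 50% | 0% | 95% | 95.0% |
| 2 | 33% | +5% | 90% | 97.5% |
| 4 | 20% | +15% | 83% | 98.75% |
| 9 | 10% | +40% | 68% | 99.4% |
| 19 | 5% | +90% | 50% | 99.7% |

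At r = 0 the error is -5%, so between r = 0 and r = 2 the net error stays within 5% either way.

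**Illustrations with assumed movement numbers.**
- 40 throws and 200 others (r = 5): 0.95 x 40 + 0.05 x 200 = 38 + 10 = 48, an error of +20%, with PPV 38/48 = 79%.
- 10 throws and 200 others (r = 20): 9.5 + 10 = 19.5, an error of +95%, with PPV 9.5/19.5 = 49%.
- No throws and 100 others: 5 false throws, and a relative error that is undefined.

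**What sensitivity and PPV together guarantee.** Device count / true count = sensitivity / PPV. With both at least 95%, the pooled ratio is at least 0.95/1 = 0.95 and at most 1/0.95 = 1.053, whatever the value of r.

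**Whether count error should also be a pass limit.** Take a device with 95% sensitivity and expected false throws equal to 5% of true throws, with independent movements. Its expected absolute count error per child, from the exact binomial sum, is 6.7% at 10 throws, 5.2% at 20 and 3.8% at 40. A 5% limit on mean absolute error would thus be expected to fail a device that meets the other two criteria when sessions contain few throws.

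**The case against.** The case for leaving the rule alone has several parts.

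**The movement mix.** A reader might infer that throws are known to be a minority of movements, so that a material over-count follows. The documents do not support that: no section gives a number or proportion of other movements. In Phase 1 the game is described as pitches, with runs, swings and catches performed separately afterwards, and the field throws in that later set are themselves throws. The Phase 1 ratio could be below 1, where the net error lies between -5% and 0%. Even a minority of throws is not enough; the net error exceeds +5% only above r = 2. This objection stands for Phase 1. For the Pilot, a limited number of throws within a fully recorded therapy session makes a high r plausible but not established.

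**The 5% rate.** A reader might also infer that 5% of other movements will be added to the count. That is the most the rule allows, not the rate that must occur.

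**The stage.** Section 5.2.1 segments movements first and classifies them afterwards, and the limit in Section 6.3.1 is worded for detection. Classification may remove false detections. This too stands, but Section 6.3.1 sets no numerical limit for classification and none for the final count, so the gap remains.

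**The stakes and scope.** The study is exploratory, the analysis is aimed at feasibility, and pitch count is not named among the endpoints in Sections 6.1 and 6.2. Section 6.3.1 also does not say that its limits apply to the Pilot. These points limit the seriousness. They do not answer why a plan that sets a pass limit should set one that leaves its stated Pilot output untested.

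**Conclusion.** The point holds in a limited form: passing the 95%/95% rule implies nothing definite about count accuracy, because the error depends on a ratio that the plan neither states nor restricts. At the limit, the net error runs from 0% at r = 1 to +90% at r = 19, and PPV falls from 95% to 50%. These figures rest on per-movement measures, performance exactly at the limit, no further filtering after the output being judged, and assumed values of r.

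The documents do not show that the device will over-count, and they do not establish the size of any error in either phase. The finding concerns what the success rule fails to exclude. It is worth correcting because the change is small and the Pilot aim is explicit.

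**What to change.** Amend Section 6.3.1 as follows.

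1. Apply the criterion to the final throw/non-throw output, after classification, with one movement as the unit.
2. Keep sensitivity of at least 95%. For throw detection, add a pooled PPV of at least 95%, calculated at the movement mix observed in each phase. Continue to report specificity.
3. Report the count error (device minus true) for each child and phase descriptively, not as a further 5% pass limit. For sessions without throws, give the absolute number of false throws.
4. State that the true Pilot count is the study team's tally of throws during the session, noted so that each device detection can be matched to a throw. Video recording and expert review are described only for the Epic facility (Sections 5.1.6 and 6.3.2), and no reference count is described for the Pilot. Sensitivity and specificity there would need one in any case.

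The cost is a few sentences in Section 6.3.1 and a staff tally in Pilot sessions; no extra subjects are needed. The downside is a somewhat stricter, less favourable success rule wherever other movements outnumber throws.

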6.3.2 Efficacy Analysis

Data recorded from the motion capture system will be analyzed with C-Motion Research Visual 3D v5 Professional and used to derive biomechanical variables of interest when performing movements associated with overuse injuries or of interest for performance monitoring. Analysis will calculate a time series of torques, compression forces, and tension forces on joints, ligaments, and muscles of interest. A biomechanist at the Epic Sports Biomechanics research facility familiar with baseball will review video of each movements of interest (e.g. pitches) and segment movements into their constituent phases. Additionally, the biomechanist will flag any abnormalities in data such as aborted movements and instances of improper form or technique.

6.3.3 Safety Analysis

This is a minimal risk study. The Principal Investigator will be responsible for monitoring the safety of study subjects and complying with all reporting requirements. Members of the study team who perform the motion analysis will monitor subjects throughout to ensure that they do so safely. The PI and study investigators will monitor data accuracy and identify ways to resolve any problem areas.

6.4 Sample Size and Power

This is an exploratory study so no power analysis was conducted. A total of 40 patients will be enrolled study-wide. For the pilot phase, we plan to enroll 20 patients to yield 10 evalables. Additionally, based on previously reported literature, we plan to enroll a convenience sample of 20 youth baseball players in Phase 1 to yield 10 evaluable subjects, mainly consisting of pitchers, will be recruited to participate in this study. However, to account for subject withdrawal and attrition rates, study team plans to enroll additional 10 more subjects per phase.

7 SAFETY MANAGEMENT

7.1 Clinical Adverse Events

Clinical adverse events (AEs) will be monitored throughout the study.

7.2 Adverse Event Reporting

Since the study procedures are not greater than minimal risk, SAEs are not expected. If any unanticipated problems related to the research involving risks to subjects or others happen during the course of this study (including SAEs) they will be reported to the IRB in accordance with CHOP IRB SOP 408: Unanticipated Problems Involving Risks to Subjects. AEs that are not serious but that are notable and could involve risks to subjects will be summarized in narrative or other format and submitted to the IRB at the time of continuing review.

8 STUDY ADMINISTRATION

8.1 Treatment Assignment Methods

8.2 Data Collection and Management

1. **Confidentiality of Data.** A master list will be maintained separately from the data collection sheet and will contain identifiable data including subject ID, name, DOB and MRN (if applicable). The study team members will be the only individuals with access to the master list. All other data will be collected on a separate coded data collection sheet—only the study ID number will link the master sheet to the coded data sheet. Both the master list and coded data collection sheet will be password-protected excel files. Data will be managed and stored using the research-focused electronic data capture system REDCap, under an agreement with the software's development consortium, led by Vanderbilt University. REDCap supports two secure, web-based applications designed exclusively to support data capture for research studies. REDCap is a PHP web application served by Apache Tomcat over a 128 bit SSL connection using a signed certificate. The application relies on a study-specific data dictionary defined in an iterative self-documenting process that will be conducted by all members of the research team. The data dictionary is the foundation for custom case report form design and validated coding of variables. Authentication of research staff will be performed via LDAP using CHOP's enterprise Active Directory service. The application generates a complete audit trail of user activity, provides reporting, and has an automated export mechanism to common statistical packages (SAS, SPSS, Stata, R/S-Plus).
2. **Security.** The master sheet and data collection sheet will be password protected excel files kept in the secure storage network for the Division of Orthopaedics on the secure hospital server. The REDCap MySQL database is replicated in real time to a completely redundant instance of MySQL. The redundant instance is available for restoration of the primary database or for manual failover in the case of primary database failure. Time-stamped backup files are made from the replicated database daily by CHOP Research Information Systems using automated backup routines. Backup files are encrypted and transferred to a secure file server accessible only to designated personnel. A rolling seven-day window of backup files is maintained in an immediately available online state, with a larger window maintained in a compressed file archive available at a reduced speed of access. Daily destructive database backup files are stored on the database server and are deleted only after successful backup of the entire database to file. In the event of data error, loss or corruption, research personnel will work with CHOP Research Information Systems to determine the most appropriate recovery strategy. Data and backups are stored in the CHOP Research Information Systems Storage Area Network (SAN). Access to the SAN directories where data are stored will be limited to Research Information Systems personnel, with authentication performed using CHOP's enterprise Active Directory service. Consent forms from the Pilot Phase will be stored electronically on the secure orthopaedics hard drive or a hard-copy will be kept in a binder in the locked research office. Consent forms from Phase 1 will be stored in REDCap. All data collected from the throwing device or at the Epic Sports Biomechanics research

facility will be secured electronically or in locked cabinets only accessible to research personnel. Processed data collected in the Epic Sports Biomechanics research facility will be transferred to research staff at CHOP and the University of Pennsylvania as coded, password-protected excel files sent via secure email servers or CHOP's secure ShareFile functionality. Any processed or unprocessed data from the throwing device and/or Epic Sports Biomechanics analysis will be transferred to CHOP or the University of Pennsylvania before being sent via secure email servers, an encrypted flash drive, or CHOP's ShareFile function to collaborators outside of CHOP or the University of Pennsylvania where it will be stored securely in password-protected computers or drives.

3. **Anonymization, de-identification or destruction.** The information collected as part of this study will be retained until at least two years following final marketing approval for the device according to FDA data retention guidelines. At that time, the research information will either be destroyed or all the information that identifies the subject will be removed from the study results and the key destroyed.

8.3 Confidentiality

All data and records generated during this study will be kept confidential in accordance with Institutional policies and HIPAA on subject privacy and the Investigator and other site personnel will not use such data and records for any purpose other than conducting the study. Data will be maintained in REDCap or in password-protected data files on password-protected computers. Data transfers will be limited to within the study team and will utilize encrypted flash drive, secure email providers, and/or CHOP's secure ShareFile function.

No identifiable data will be used for future study without first obtaining IRB approval or a determination of exemption". The investigator will obtain a data use agreement between the provider (the PI) of the data and any recipient researchers (including others at CHOP) before sharing a limited dataset (PHI limited to dates and zip codes).

8.4 Regulatory and Ethical Considerations

8.4.1 Data and Safety Monitoring Plan

The principal investigator will monitor data and safety throughout the duration of the study. There is minimal safety risk associated with participation in this protocol, but the study team will immediately notify the PI if any safety issues do arise. The PI and study team will monitor data accuracy and identify ways to resolve any problem areas.

8.4.2 Risk Assessment

The risks of this study are no greater than minimal. Risks to study subjects are breach of privacy and/or breach of confidentiality. There is a minimal risk that survey questions may make subjects uncomfortable, but subjects do not have to answer any questions that make them feel uncomfortable. There is also a minimal risk that subjects may become injured while being asked to perform different throws and movements typical of physical therapy regimens or youth baseball play. However, this risk will be minimized because subjects will be under the supervision of a trained physical therapist and subjects will be able to

discontinue any throw/movement that makes them uncomfortable. Finally, there may be a risk of skin irritation from wearing the PhysSens device.

8.4.3 Potential Benefits of Trial Participation

There are no direct benefits to the subject related to this study.

8.4.4 Risk-Benefit Assessment

The risks of this study are no greater than minimal. While there is minimal risk to subjects due to accidental disclosure of PHI, this risk is minimized through the techniques outlined in the “Data Collection and Management” section.

8.5 Recruitment Strategy

Participants for the Pilot Phase will be recruited from orthopaedics physical therapy clinics at CHOP. Potential subjects will be identified by a member of the study team based on screening sports medicine physical therapy clinic schedules against the inclusion/exclusion criteria. Patients who are qualified for the study (based on the inclusion/exclusion criteria) will be approached and consented during their physical therapy visit.

Participants for Phase 1 will be recruited from multiple sources including solicitation letters sent to local youth sport organizations, fliers placed in the Sports Medicine Centers throughout CHOP organization, and or personal solicitation via email, phone, or in-person contact. Patients who are qualified for the study (based on inclusion/exclusion criteria) and who respond to solicitation or other recruitment strategies will be consented via e-consent processes using REDCap and will have the opportunity to ask questions during a phone call with a member of the study team prior to signing the eConsent. At the biomechanics laboratory for throwing performance housed at Epics Sports Biomechanics, the subjects will undergo additional data collection within the 3-D motion laboratory in order to augment training data and re-estimate the accuracy of the various algorithmic components.

For the Pilot Phase, a convenience sample of 20 youth athletes will be recruited to participate. Recruitment will stop when 10 evaluable subjects have undergone data collection.

For Phase 1, a convenience sample of 20 youth baseball pitchers, will be recruited to participate in this study. Recruitment will stop when 10 evaluable subjects have undergone data collection.

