3 INVESTIGATIONAL PLAN

3.1 General Schema of Study Design

This study will occur in two phases with two different subject groups. The Pilot Phase will include 10 evaluable subjects and occur in the sports medicine physical therapy clinic at the Children's Hospital of Philadelphia. Subjects will be asked to perform simple throwing movements as part of or in addition to their rehabilitation regimen. This will test the ability of the prototype device to detect basic movements.

Phase 1 will include 10 evaluable subjects and occur at the Epic Sports Biomechanics research facility. Subjects will partake in a simulated baseball game while wearing the prototype device and additional baseball-related movements while being tracked by the Epic Sports Biomechanics research facility's infrared sensors. The goal of this phase is to create and refine a more robust algorithm for the device that can track various throwing movements and track potential injurious forces or poor techniques.

This study is a prospective reliability study.

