3.3 Study Population

3.3.1 Inclusion Criteria

Pilot Phase

- 1) Males or females age 8 to 14 years
- 2) Presenting to CHOP Physical Therapy Clinic for rehabilitation of injury that does not impede their ability to perform basic throwing movements.

Phase 1

- 1) Males or females age 8 to 14 years
- 2) Involved in official baseball team and primarily plays as the pitcher

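### Phase 1 sets no age spread for its ten evaluable children and judges success without regard to age, so a verdict could rest on part of the 8-14 range or hide a large error in one or two children

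*Combined protocol and SAP*

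**What the plan says.** Both phases admit "Males or females age 8 to 14 years" (3.3.1). Phase 1 adds one further inclusion criterion: "Involved in official baseball team and primarily plays as the pitcher". Section 6.4 says "we plan to enroll a convenience sample of 20 youth baseball players in Phase 1 to yield 10 evaluable subjects" and explains that the additional ten per phase allow for withdrawal and attrition. Section 8.5 repeats the convenience sample, "For Phase 1, a convenience sample of 20 youth baseball pitchers, will be recruited to participate in this study", but makes the end of recruitment depend on a count alone: "Recruitment will stop when 10 evaluable subjects have undergone data collection". The sources are "solicitation letters sent to local youth sport organizations, fliers placed in the Sports Medicine Centers throughout CHOP organization" and personal solicitation. No section sets a quota, a minimum or a recruitment target by age.

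On success, 6.3.1 says "Biomechanical value prediction models will be considered successful if error distributions have mean and standard deviation of less than 5% and 10% respectively", both percentages being relative to nominal, and requires 95% sensitivity and specificity for detection. It specifies k-fold cross-validation but not how the folds are formed, and it gives no breakdown by age or child. Date of birth is collected in the Phase 1 demographic survey (5.1.4), but no analysis uses age.

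**The concern.** These ten children supply the facility data from which the movement classifier, the phase model and the regression to joint loads are learned (5.2.1). Section 8.5 adds that the facility sessions also serve to re-estimate the accuracy of the components. The Pilot Phase cannot fill an age gap, because its sessions have no motion capture (3.1.2, 5.1.5). Section 5.1.2 treats range of motion, strength and humeral retrotorsion as possible influences on throwing technique, so which children are sampled can affect what the models learn.

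Cross-validation measures performance only among the children recruited. An age group with no child is untested, and one with a single child contributes about a tenth of the pooled figure. The device is meant for youth baseball players generally (section 2). A bare statement that the models met their limits would therefore give the reader no means of seeing which ages it covers, or whether a child of a given age was badly predicted.

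**Working it through.** **The plan's own figure.** Ten evaluable children with half lost gives 10 / (1 − 0.5) = 20 per phase and 40 in total, as 6.4 states. This checks the arithmetic only, since 6.4 reports no power analysis.

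**Inputs from the documents.** 10 evaluable children in Phase 1 (3.1, 6.4, 8.5); ages 8 to 14, which is seven single years (3.3.1); limits of 5%, 10% and 95% (6.3.1).

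**Inputs assumed.** The share p of responders aged 8-10; the within-child error SD s; equal weight per child; errors pooled over all children, which is the natural reading of 6.3.1 as it describes no other way of combining them.

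**Step 1: how often is the youngest group absent or nearly so?** With the number of children aged 8-10 distributed as Binomial(10, p):

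- P(none) = (1 − p)^10
- P(at most one) = (1 − p)^10 + 10p(1 − p)^9

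| p | P(none) | P(at most one) |
|---|---|---|
| 10% | 35% | 74% |
| 20% | 11% | 38% |
| 30% | 3% | 15% |
| 3/7 = 43% (even spread over seven years) | 0.4% | 3% |

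Even under an even spread, any given single year of age is missing with probability (6/7)^10 = 21%.

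**Step 2: how large an error passes the regression limits?** Let a fraction f of the children carry bias b (in % of nominal) and let the rest be unbiased.

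- Pooled mean = f·b, which must be below 5.
- Pooled SD = √(s² + f(1 − f)b²), which must be below 10.
- The SD limit gives b < √[(100 − s²) / (f(1 − f))].

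One child in ten, f(1 − f) = 0.09:

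- s = 5%: √(75 / 0.09) = 28.9%, pooled mean 2.9%
- s = 8%: √(36 / 0.09) = 20.0%, pooled mean 2.0%
- s = 9.5%: √(9.75 / 0.09) = 10.4%, pooled mean 1.0%

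Two children in ten, f(1 − f) = 0.16:

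- s = 5%: √(75 / 0.16) = 21.7%, pooled mean 4.3%
- s = 8%: √(36 / 0.16) = 15.0%, pooled mean 3.0%
- s = 9.5%: √(9.75 / 0.16) = 7.8%, pooled mean 1.6%

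Three children in ten at s = 8%: √(36 / 0.21) = 13.1%, pooled mean 3.9%.

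The mean stays below 5% in every case shown, so the SD limit is the one that binds.

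**Step 3: the same question for detection.** Assume nine children at 98% sensitivity and equal numbers of movements per child. Pooled sensitivity reaches 95% when 0.9 × 0.98 + 0.1x = 0.95, so x = (0.95 − 0.882) / 0.1 = 68%. With two such children, x = (0.95 − 0.784) / 0.2 = 83%.

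**The case against.** The strongest reply is that this is an exploratory study with no power analysis (6.4), analysed to judge feasibility (6.3.1). An openly labelled convenience sample of ten is ordinary in that setting. This stands as a defence of the sampling method and of the sample size. It does not settle the scope of the verdict, because 6.3.1 still calls models successful against fixed limits.

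Several stronger readings are tempting, and the documents do not support them:

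- A reader might infer that responders will be mostly older, because they must be on an official team and primarily pitch. The documents do not give the age mix, and the recruitment sources show no tilt. Under an even spread, near-absence of ages 8-10 is unlikely (3%).
- A reader might infer that throwing mechanics change most over these ages. Section 5.1.2 links physical measures to technique but says nothing about age.
- A reader might infer that the plan claims success for every age from 8 to 14. No section says so. The wide scope follows only from the eligibility range, the intended users and limits stated without an age restriction.
- A reader might infer that 20 enrolments for 10 evaluable children leave room to choose the mix. Section 6.4 assigns the extra ten to attrition.

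A hard quota is also open to fair objection. At the planned 50% yield, three evaluable children aged 8-10 need about 3 / 0.5 = 6 enrolled. That means about 6 / 0.10 = 60 responders if 10% are that young, or 6 / 0.20 = 30 at 20%. Nor would a quota cure masking: at s = 8%, three children with a 13% bias still pass. Showing results child by child is what exposes such an error.

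**Conclusion.** The point holds as a gap in coverage and reporting. Nothing in the plan secures a spread of ages among the ten children, and nothing in the success rule would reveal a poor result at one age.

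How likely poor coverage is depends on an age mix that the documents do not give: 3% to 74% for at most one child aged 8-10, over the shares examined. These figures treat the ten ages as independent draws.

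The masking does not depend on a skewed mix and applies to a child of any age. Its size does depend on assumptions: an unknown within-child SD (tolerated bias of about 29%, 20% or 10% for one child), equal weights, and no bias in the other nine. The figures show what the pooled rule would let through; they do not predict that such an error will occur. The point merits a change to the plan, but it does not invalidate the study.

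**What to change.** In 8.5, with a matching line in 6.4, add a soft recruitment target applied at screening for children across the age range. One example is to aim for about three evaluable children each at 8-10, 11-12 and 13-14, which uses nine of the ten places. State that meeting the target is not a condition for completing the study. The bands are illustrative and the team may prefer others.

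In 6.3.1:

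- Split the cross-validation folds by child. Otherwise movements from one child can fall in both training and test sets, and that child's error is not truly held out.
- Show each child's held-out error and sensitivity by age beside the pooled figures, using the date of birth already collected.
- State the success conclusion only for the ages observed, and name any gap.

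The cost is protocol wording, possibly slower recruitment of the youngest children, and a narrower claim if an age group is missing. The planned sample size does not change. With about three children per band, the by-age figures are descriptive only and should be labelled so.
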